## **2.1 Protocol Deviation:**

The Principal Investigator must sign the protocol and its amendments (if any) before initiating the study at a particular site. The Investigator will make all reasonable efforts to comply with the written protocol. Protocol modifications to ongoing studies that affect the safety of subjects or that alter the scope of the investigation, the scientific quality of the study, the experimental design, dosing, study assessments, the number of subjects exposed to test drug, or subject selection criteria must be made only after consultation between Xeris and the Investigator. All protocol modifications must be reviewed and approved by the IRB/IEC before the revised protocol can be implemented. Emergency revisions that eliminate an apparent hazard to subjects do not require preapproval by the IRB/IEC. However, the IRB/IEC must be notified in writing as soon as possible after the modification has been made. A copy of this communication must be forwarded to Xeris. All departures from the protocol must be fully documented in the source documents and the eCRFs of the subjects involved. Protocol deviations will be tracked in an electronic system implemented by the Sponsor or designated representative. Protocol Deviations

will be summarized as per the impact (Major/Minor) and category across the treatments throughout the different phases of the study. This classification is designated by the Sponsor and documented prior to locking and unblinding the study.

A summary of protocol deviations will be created for the CRC phase and Outpatient phase of the study using the ITT and Safety population for each phase.

A listing of subjects with Protocol Deviations (PD) will be provided for both CRC phase and Outpatient phase.

## **2.2 Handling of Missing Data:**

Imputation of missing data will not be performed.

To handle missing or partial AE and concomitant medication dates, the following rules will be applied.

For partial start dates:

1. If the year is unknown, then do not impute the date but assign a missing value.
2. If the month is unknown, then assign “January.”
3. If the day is unknown, then assign “01.”

For partial end dates:

4. If the year is unknown, then do not impute the date but assign a missing value.
5. If the month is unknown, then assign “December.”
6. If the day is unknown, then assign the last day of the month.

After implementing the rules above, to determine whether AEs (or medications) with missing start or stop dates are pretreatment or on/after treatment, the following strategy will be used:

1. If the start date and stop date are both missing, then the most conservative approach is taken and the AE (or medication) is considered to be treatment emergent (or concomitant medication).

2. If the start date is missing but the stop date is not missing and is on or after the day of study dose administration, then the most conservative approach is taken and the AE (or medication) is considered to be treatment emergent (or concomitant medication).
3. If the start date is missing but the stop date is not missing and is before the day of study dose and after the date of signed informed consent, then the AE (or medication) is considered to be before treatment (or prior medication).
4. If the start date is not missing but the stop date is missing, then the most conservative approach is taken, and medication is considered to be concomitant while the AE is defined by start date.

If the Adverse Event Relationship flag is missing, the relationship for adverse event will be defined as related. If the Adverse Event Severity flag is missing, the severity for adverse event will be defined as severe.

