### **Baseline for Outpatient Phase:**

The Baseline for Outpatient Phase is defined as the latest assessment prior to the first administration of the study drug in the Outpatient Phase for the analysis pertaining to Outpatient Phase, unless otherwise stated.

If the assessment occurs on the same day as the first study drug administration for either of the phases, then the time of assessment should be compared to the time of first dose administration for both CRC and Outpatient Phase.

Baseline will be calculated as the average of the blood glucose measurements (BGMT) at: -15 minutes and just before the exercise session (Time 0).

**Change from Baseline:** The change from baseline values will be calculated as post baseline value minus the baseline value.

If BGM readings are missing from the CRC phase, the YSI readings can be used.

**Shift from Baseline:** The shift from baseline is defined as a change in categorical variable from baseline to subsequent visits for each subject.

**Percentage Change from Baseline:** The percentage change from baseline is defined as the ratio of change (Analysis value – Baseline value) and baseline value expressed in terms of percentage.  
% Change from Baseline =  $((\text{value} - \text{baseline}) / \text{baseline}) * 100$ ;

**Treatment Emergent Adverse Event (TEAE):** TEAE is any AE does not present prior to the initiation of IMP (Investigation Medicinal Product) administration at CRC phase or any event already present that worsens in either intensity or frequency following exposure to the IMP at CRC phase.

An SAE is any AE that results in death, is life-threatening (this refers to an event in which the subject was at risk of death at the time of the event; it does not refer to an event that hypothetically might have caused death had it been more severe), requires inpatient hospitalization or prolongation of existing hospitalization, results in persistent or significant

disability/incapacity, is a congenital anomaly/birth defect, is medically important (this refers to an event that may not be immediately life-threatening or result in death or hospitalization, but may jeopardize the subject or may require intervention to prevent any of the SAEs defined above).

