#### **4.3.9 Safety Analysis**

##### **Adverse Events:**

All analyses will be conducted in the safety population. Adverse events will be recorded from the time of consent until completion of study. The number and percentage of subjects with AEs will be displayed by body system and preferred term (MedDRA), by study treatment. Summaries in terms of severity and relationship to Study Drug will also be provided. All SAEs will be summarized in a similar manner. Participant listings of all AEs causing discontinuation of study medication and SAEs will be produced.

All AEs will be listed for individual subjects showing both verbatim and preferred terms. Separate summaries of treatment emergent SAEs and TEAEs related to Study Drug will be generated.

AEs will be summarized separately during the CRC treatment visits. Any AE that occurs after administration of study drug at Visit 3 and prior to administration of the alternate study drug at Visit 4 will be treatment emergent with respect to the study drug received at Visit 3. Any AE that occurs after administration of study drug at Visit 4 and prior to the first administration of study drug in the out-patient phase will be treatment emergent for the study drug received at Visit 4. Any event reported on the eCRF that occurs at the time of or after the initiation of Study Drug in the out-patient phase is defined as treatment-emergent for that study drug. Additionally, an AE that was reported to have started on Day 1 without an associated onset time is assumed to have

occurred after the initiation of Study Drug. Hence, AEs occurring on Day 1 with no associated onset time are assumed to be treatment emergent.

SAEs associated with a protocol specified procedure and occurring after the time of consent but before administration of first dose of Study Drug are defined as Non-Treatment Emergent AEs (NTEAE).

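### Partial adverse-event start dates are set to the 1st or to January without regard to dosing, so some post-dose events are classed as pre-treatment or credited to an earlier study drug

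*SAP*

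**What the plan says.** SAP Section 2.2 works in two steps. The first completes partial dates. In the start-date list, "If the month is unknown, then assign" January, and "If the day is unknown, then assign" 01; only an unknown year leaves the date missing. No dose date enters this step.

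The second step begins "After implementing the rules above, to determine whether AEs (or medications) with missing start or stop dates" and then sorts events into pre-treatment and on-treatment. Its protective defaults are conditional on a missing start date: "If the start date and stop date are both missing, then the most conservative approach is taken", and likewise "If the start date is missing but the stop date is not missing and is on or after the day of study dose administration". Where the start date is present and the stop date is not, "medication is considered to be concomitant while the AE is defined by start date".

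SAP Section 2.4 supplies the test: "TEAE is any AE does not present prior to the initiation of IMP (Investigation Medicinal Product) administration at CRC phase", or an event already present that worsens after exposure. SAP Section 4.3.9, like Protocol Section 12.4.4, then credits each event to the Visit 3, Visit 4 or outpatient drug according to when it occurred relative to those doses. One safeguard is given there: "AEs occurring on Day 1 with no associated onset time are assumed to be treatment emergent". Protocol Section 12.4.10 leaves missing-data methods to the SAP.

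**The concern.** A start date with a known year is no longer missing once it has been completed, so the protective defaults cannot reach it. The event is then judged on a date that is the earliest the known parts allow. An event known to have started in the dosing month can fall out of the treatment-emergent (TEAE) summaries, while an event about which nothing is known is included. More information gives a less cautious result. This also runs against the rest of Section 2.2, where a missing relationship becomes related and a missing severity becomes severe.

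Two results are at stake. TEAE counts can only be lowered by this mechanism. In addition, because the CRC sessions are 2 to 28 days apart and the outpatient period can start on Day 4, several dose boundaries often fall in the same or adjacent months. An early imputed date can then move an event from one drug to another, including between glucagon and placebo.

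**Working it through.** The plan states no figure on this point, so there is none to reproduce. The check applies the Section 2.2 rules literally and then the rules in Sections 2.4 and 4.3.9. All calendar dates below are assumed for illustration.

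**1. Loss from the TEAE tables.** Visit 3 dose 10 September 2019, Visit 4 dose 17 September, first outpatient dose 19 September.
- True onset 12, 18 or 25 September, day unknown: imputed 1 September, before first dose, so not a TEAE.
- The same events, month unknown: imputed 1 January 2019, so not TEAEs.
- True onset 20 October, day unknown: imputed 1 October, still a TEAE of the outpatient drug.

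Had the first dose been on the 1st, the imputed date would be Day 1 with no time, and the Day 1 safeguard would keep the event.

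**2. Wrong drug.** Visit 3 on 20 September, Visit 4 on 4 October, first outpatient dose 7 October. True onset 15 October, day unknown: imputed 1 October, which lies between Visits 3 and 4. The event is credited to the Visit 3 drug instead of the outpatient drug.

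**3. Share moved before first dose, given a post-dose onset and a partial start date.** Assumptions: first doses spread evenly over the 365 days from 1 July 2019, and onset uniform within each window.

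| Onset window (days after first dose) | Day unknown | Month unknown |
|---|---|---|
| First 7 days | 87% | 99% |
| 0 to 27 | 53% | 96% |
| 0 to 112 | 13% | 84% |

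The month-unknown column depends on how the trial straddles the new year. If the reported year follows the year of first dose, the imputed 1 January is after first dose and the event stays a TEAE.

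**4. Attribution, day unknown.** Same spread of first doses, with an 84-day outpatient period. The lag from Visit 4 to the first outpatient dose is assumed to be 1, 2, 3 and 3 days in the four rows.

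| Gap, Visit 3 to 4 (days) | Visit 4-period AEs credited to the Visit 3 drug | Outpatient AEs credited to a CRC drug |
|---|---|---|
| 2 | 6% | 3% |
| 7 | 23% | 9% |
| 14 | 46% | 14% |
| 28 | 91% | 18% |

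These are events that remain TEAEs but under the wrong drug. They come on top of the events lost as pre-treatment.

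**5. All AEs in the first-dose month, including truly pre-dose ones.** AEs are recorded from consent, and screening opens up to 28 days before dosing, so some events in that month did precede the dose. Take a 30-day month, with dose day d and onset day both uniform.
- Post-dose but imputed pre-dose: sum over d = 2 to 30 of (31 − d), divided by 900 = 435/900 = 48%.
- Truly pre-dose and imputed pre-dose: sum over d = 2 to 30 of (d − 1), divided by 900 = 435/900 = 48%.
- Dose on the 1st, correctly kept: 30/900 = 3%.

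Consent within the month, or a higher AE rate on drug, would raise the first share.

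**The case against.** The best defence is that few events are exposed. CRC dosing is in clinic with an AE assessment at the visit, outpatient AE review is every two weeks, and Protocol Sections 13.1.4 and 13.1.6.1 provide for resolving missing data with the site. Under that schedule an on-treatment event with an unknown month should be rare. Nor does the event vanish: all AEs are listed, and the SAE tables (14.3.1.3.1 and 14.3.1.3.2) are separate from the treatment-emergent SAE tables. CRC injection-site reactions are also summarised from the Draize scale and the discomfort questionnaire, whatever the AE date. All of this stands, and it limits the expected effect. It does not cure the rule. Onset of AEs is not among the listed paper-diary items (Protocol Section 10.4.1), and the Draize scale and questionnaire are used only at Visits 3 and 4, so outpatient tolerability rests largely on AE reports.

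Three stronger readings are tempting, and the documents do not support them.
- A reader might take 29/30, or 97%, as the share of partial-date events misclassified. That is only the chance that a dose day uniform over 30 days is not the 1st. It ignores truly pre-dose events and onsets in later months.
- A reader might infer that every event with an unknown month is lost. An event reported in the following year can stay a TEAE.
- A reader might say that Section 2.2 contradicts itself. Its sequence is explicit, so the fault is uneven caution and not conflicting instructions.

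**Conclusion.** The point holds within limits. The stated rule gives a wrong classification for post-dose AEs with an unknown day in the calendar month of first dose, or an unknown month in the year of first dose, unless the dose fell on the imputed date. It can also credit a remaining TEAE to an earlier drug when the imputed date falls before the Visit 4 dose or the first outpatient dose. No other passage in either document corrects this. With the day unknown, onsets in later months generally stay TEAEs.

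The percentages above are conditional on a partial start date and on the assumed spread of doses and onsets. They do not forecast how many events will be lost, because the documents do not say how many partial dates there are. Only the direction of the effect on TEAE counts is certain. With 48/3 = 16 subjects per outpatient arm, one subject moves a TEAE percentage by 1/16, about 6 points, so even a few such events could show. The expected effect is modest, but the rule should be changed because it is wrong where it bites and cheap to repair.

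**What to change.** Amend SAP Section 2.2, for AEs only, before unblinding:

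- If the known parts of the start date are compatible with onset on or after the first dose, and the stop date does not show that the event ended before that dose, treat the AE as treatment emergent.
- If the known parts are compatible with more than one treatment period (Visit 3, Visit 4, outpatient), assign the AE by one fixed rule. One example is the latest period whose first dose is compatible with the known start-date parts and is not after the stop date.
- Otherwise keep 01 and January, and keep them for concomitant medications.

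Imputing a phase's first-dose date would not be enough. The CRC phase has two doses of different drugs, so a Visit 4 event would go to the Visit 3 drug, and a month shared with the first outpatient dose would leave two candidate dates.

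Under the first rule, no post-dose AE with a partial start date is moved before first dose. The cost is a few sentences, a few lines of code and a slightly higher TEAE count, because some truly pre-dose events will be included. In the setting of step 5 that is at most the other 48%, less those whose stop date precedes the dose. The example attribution rule also errs, towards the later drug: in the September example, an AE of 12 September with unknown day and no stop date would go to the outpatient drug, and with a stop date of 15 September it would go correctly to the Visit 3 drug. Any single rule has such an error. What matters is that it is chosen blind and stated.

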### **2.3 Treatment Group Labelling in TFLs:**

The Treatments in the CRC phase will be labelled as “Treatment A” and “Treatment B”

The Treatments in the Outpatient phase will be labelled as “Treatment A,” “Treatment B,” “Treatment C” in the footnote for the respective TFLs. A Footnote will be added for the treatment columns as below:

“Treatment A” = “Glucagon RTU (30 µL active - 0.15 mg) with 50% insulin pump reduction”

“Treatment B” = “Placebo injection (30 µL vehicle) with 50% insulin pump reduction”

“Treatment C” = “Glucagon RTU (30 µL active - 0.15 mg) without 50% insulin pump reduction”

### **2.4 Definition**

#### **Baseline for CRC Phase:**

The Baseline for the CRC Phase is defined as the latest assessment prior to the first administration of the study drug in the CRC Phase for period 1, and the first assessment prior to the first administration of the study drug in period 2 for the analysis pertaining to CRC Phase, unless otherwise stated.

Baseline will be calculated as the average of the blood glucose measurements at: -15 minutes (both YSI and BGM) and Time 0 (immediately before exercise) (both).

### **Baseline for Outpatient Phase:**

The Baseline for Outpatient Phase is defined as the latest assessment prior to the first administration of the study drug in the Outpatient Phase for the analysis pertaining to Outpatient Phase, unless otherwise stated.

If the assessment occurs on the same day as the first study drug administration for either of the phases, then the time of assessment should be compared to the time of first dose administration for both CRC and Outpatient Phase.

Baseline will be calculated as the average of the blood glucose measurements (BGMT) at: -15 minutes and just before the exercise session (Time 0).

**Change from Baseline:** The change from baseline values will be calculated as post baseline value minus the baseline value.

If BGM readings are missing from the CRC phase, the YSI readings can be used.

**Shift from Baseline:** The shift from baseline is defined as a change in categorical variable from baseline to subsequent visits for each subject.

**Percentage Change from Baseline:** The percentage change from baseline is defined as the ratio of change (Analysis value – Baseline value) and baseline value expressed in terms of percentage.  
% Change from Baseline =  $((\text{value} - \text{baseline}) / \text{baseline}) * 100$ ;

**Treatment Emergent Adverse Event (TEAE):** TEAE is any AE does not present prior to the initiation of IMP (Investigation Medicinal Product) administration at CRC phase or any event already present that worsens in either intensity or frequency following exposure to the IMP at CRC phase.

An SAE is any AE that results in death, is life-threatening (this refers to an event in which the subject was at risk of death at the time of the event; it does not refer to an event that hypothetically might have caused death had it been more severe), requires inpatient hospitalization or prolongation of existing hospitalization, results in persistent or significant

disability/incapacity, is a congenital anomaly/birth defect, is medically important (this refers to an event that may not be immediately life-threatening or result in death or hospitalization, but may jeopardize the subject or may require intervention to prevent any of the SAEs defined above).

**Qualified Exercise Session:** For inclusion in the statistical analysis for the per protocol population (defined in section 4.1) a qualified exercise session will be defined. Exercise sessions will be performed in both the CRC and Outpatient phases. In the CRC phase, a qualified exercise session will be defined as the subject having (1) a blood glucose value of 100-180 mg/dL (5.56 - 10 mmol/L) prior to starting exercise, (2) completed 45 minutes of exercise (not including breaks), (3) achieved a target heart rate of 80% of maximum calculated heart rate at least once during the workout session, and (4) fasted at least 8 hours prior to that exercise session.

Primary analysis in the CRC Phase will be based on the above definition of qualified exercise session. Additional subgroup analysis will be applied to analyze exercise sessions in which subjects achieved a target heart rate of 80% of maximum calculated heart rate for 30% and 50% of the exercise time.

In Outpatient phase, a qualified exercise session will be defined as the subject having (1) a confirmed blood glucose value of 100-180 mg/dL (5.56 - 10 mmol/L) prior to starting exercise, (2) self-administered the study drug no more than 10 minutes prior to exercise (five minutes is the target), (3) conducted a protocol allowed exercise for moderate to high intensity for at least 30 minutes and no longer than 75 minutes, and (4) achieved a target heart rate of 80% of maximum calculated heart rate at least once during the session. If a subject has more than one exercise session in a day that is deemed a qualified exercise session, only the first qualified exercise session that day will be used in the analysis.

Primary analysis in the Outpatient Phase will be based on the above definition of qualified exercise session. Additional subgroup analysis will be applied to analyze exercise sessions in which subjects achieved a target heart rate of 80% of maximum calculated heart rate for 30% and 50% of the exercise time.

**Target Heart Rate:** Per protocol, the goal is to achieve a target of 80% of maximum calculated heart rate during the session as shown by the following equation:

- Target Heart Rate =  $0.80 \times (220 - \text{Age in Years})$

**Overnight Hypoglycemia:** Throughout the study, overnight hypoglycemia will be defined as any instance of a subject's CGM reading changing from being above 70 mg/dL ( $> 3.89 \text{ mmol/L}$ ) to at or below 70 mg/dL ( $\leq 3.89 \text{ mmol/L}$ ) between Midnight and 6am (T00:00 – T06:00). Please note this definition will enable analysis of multiple instances in a given night.

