## Exploratory Objectives

1. To evaluate the glycemic time in range associated with exercise sessions and post exercise.
2. To evaluate the impact of Glucagon RTU (Glucagon Injection) on the quantity of glucose tabs used over time during exercise sessions.
3. To evaluate weight loss or weight maintenance over time.
4. To examine food intake both before and after exercise.
5. To examine the effect of exercise and Glucagon RTU on overnight hypoglycemia following episodes of exercise.
6. To evaluate the effects of exercise and Glucagon RTU use upon changes in hemoglobin A1c.
7. To evaluate the intensity and duration of the frequent exercise sessions.
8. To evaluate overall frequency of aerobic exercise over study period.
9. To evaluate effects on exercise duration and intensity as well as daily activity metrics.

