## 2. STATISTICAL AND DATA ANALYSIS CONSIDERATION

The statistical analyses will be performed by EmpiriStat, Inc., using SAS Version 9.3 (or higher). All tables, listings and figures (TLFs) will be produced in landscape format. In general, all data will be listed by the subject and visit/time point where appropriate.

Data will be summarized by treatment/treatment sequence and by period where appropriate. The total number of subjects in the study group (N) under the stated population will be displayed in the treatment sequence/treatment header of summary tables.

Data will be summarized using descriptive statistics for continuous variables. Unless otherwise stated, descriptive statistics will include number of subjects, mean, standard deviation, minimum, median and maximum. In case of  $n < 2$ , where n indicates the number of evaluable subjects at the particular time point, only n, mean, minimum and maximum will be displayed. The statistic "Missing" will also be evaluated by enumerating the number of missing entries/subjects, if any at that visit, and presented as a summary statistic only for the resulting time points.

**Decimal Precision Convention:** The minimum and maximum statistics will be presented to the same number of decimal places as the original data. The mean and median will be presented to one more decimal place than the original data, whereas the standard deviation will be presented to two more decimal places than the original data.

In summary tables of categorical variables, counts and percentages will be used. The count [n] indicates the actual number of subjects with a particular value of a variable or event, which should always be less than or equal to the total number of subjects in the respective treatment sequence [N]. Percentage will be obtained by:  $\% = (n/N)*100$ . Unless otherwise stated, all percentages will be expressed to one decimal place.

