#### **4.3.8 Exploratory Analysis:**

Glucose levels within range, >180 mg/dl, >250 mg/dl will be measured and analyzed as the mean incremental area under the curve (AUC(0-5hrs) in minutes\*mg/dL) during exercise.

Time and Proportional time (percentage within range, >180 mg/dl, >250 mg/dl) will be calculated and treatment difference will be calculated using ANOVA/Kruskal–Wallis test, based on whether the data is normally distributed or not respectively.

Generally, unless otherwise stated, the mean incidence rates will be compared using the T tests/ ANOVA or ANCOVA models using treatment arm at Outpatient phase, treatment sequence, obtained by combining the received treatments at CRC and Outpatient phase, sex as factors with, if applicable, age and weight as covariates.

Glucose tablet utilization during exercise, food (carbohydrate) intake pre/post exercise, number of exercise sessions completed across the 3 outpatient treatment arms , number of minutes exercised per week, number of calories burned per exercise sessions, number of steps, distance

covered, heart rate, floors climbed and change from Baseline in body weight will be compared for the treatment arms using T tests/ ANOVA at CRC/ Outpatient phase.

Incidence of overnight hypoglycemia will be compared for the treatment arms using Chi-Square/Fisher's exact tests at CRC/ Outpatient phase.

HbA1c data will be summarized using descriptive statistics (n, mean, SD, median, min, and max) for each scheduled study assessment, as well as change from baseline, will be summarized using ITT and PP Population.

Example of SAS syntax code that can be used for exploratory analysis is provided in APPENDIX 3.

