#### 4.6.2 APPENDIX 2. Example of SAS syntax code for secondary endpoint analysis.

The following macro can be used for the calculation of area over the curve (AOC):

```
%macro auc (dsn);
  data auctree;
    set &dsn;
    if concentration = 0 and time > tlast then delete;
    x = time;
    y = concentration;
    xpre = lag(x);
    ypre = lag(y);
    xdif = x - xpre;
    if x <= tmax or y = ypre or y =0 or ypre = 0 then do;
      auc = xdif * (( y + ypre ) / 2 );*linear rule;
    end;
    else do;
      auc = xdif * ((y - ypre) / log (y / ypre));
    end;
  run;
```

```

      end;
run;

proc summary data = auctree noprint;
  var auc;
  output out = aucest sum = auCL;
run;

proc sort data = auctree out = part1 nodupkey ;
  by subject ;
run;
data AUCs&i (keep = subject period auCL);
  merge part1 aucest;
run;
%mend auc;

```

The following macro can be used to perform estimation according to Trapezoidal Rule:

```

%macro trap(a,b,n, function);
  data f1;
    do i = 0 to &n ;
      if i = 0 then do;
        x = &a ;
        y = ((&b - &a)/&n )*( &function / 2 );
        output;
      end;
      else if i = &n then do;
        x = &b ;
        y = ((&b - &a)/&n )*( &function / 2 );
        output;
      end;
      else do;
        x = ( &a + i * (( &b - &a) / &n ) );
        y = ((&b - &a) / &n) * &function;
        output;
      end;
    end;
  end;
run;
proc summary data=f1;
  var y;
  output out=p1 sum=areau;run;
proc print data=p1;
run;
%mend;

```

The Chi-Square/Fisher's exact test can be done using the following SAS code example:

```

PROC FREQ DATA = data;
  TABLES param*trt / CHISQ FISHER EXPECTED;

```

```
WEIGHT count;
RUN;
```

Kruskal Wallis test can be performed in SAS using the following reference code:

```
PROC NPAR1WAY DATA=soil WILCOXON;
  CLASS location;
  EXACT WILCOXON / MC;
  VAR claypct;
RUN;
```

T test within the cross over design in CRC phase can be done with the help of the following reference code:

```
PROC TTEST DATA=data PLOTS=interval;
  VAR aval1 aval2 / CROSSOVER = (TrtA TrtB);
RUN;
```

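### The overnight hypoglycemia definition misses lows already present at midnight, counts repeat crossings and is not tied to post-exercise nights, and its chi-square/Fisher test has no stated unit and ignores the CRC pairing

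*SAP*

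**What the plan says.** **Definition (SAP 2.4, Overnight Hypoglycemia).** "overnight hypoglycemia will be defined as any instance of a subject's CGM reading changing from being above 70 mg/dL" to 70 mg/dL or lower, "between Midnight and 6am". It is introduced as applying across the whole study. It then adds: "Please note this definition will enable analysis of multiple instances in a given night". It gives no minimum duration, no recovery rule before a second fall counts, no rule for a subject who is low when the window opens, and no link to exercise or dosing days.

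**Objective (SAP 1.1, Exploratory Objectives).** "To examine the effect of exercise and Glucagon RTU on overnight hypoglycemia following episodes of exercise".

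**Test (SAP 4.3.8).** "Incidence of overnight hypoglycemia will be compared for the treatment arms using Chi-Square/Fisher's exact tests at CRC/ Outpatient phase". The section does not say whether the unit is the subject, the night or the crossing.

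**Related text.** For categorical tables in general, SAP 2 says: "The count [n] indicates the actual number of subjects with a particular value of a variable or event", and that this count cannot exceed N. The example code in SAP 4.6.2, "TABLES param*trt / CHISQ FISHER EXPECTED", is weighted by a count variable whose unit is not given. SAP 3 lists overnight hypoglycemia as exploratory endpoint 4. SAP 1.3.1 confirms that every subject receives both treatments in the CRC phase.

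**The concern.** Two separate things look wrong.

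First, the event rule measures onset inside a window rather than presence of a low. The longest lows can be scored as none, and small oscillations around the threshold can be scored as several. Most outpatient nights are also not nights after exercise, which dilutes the question that the objective asks.

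Second, a definition that yields many events per subject is paired with a test that needs one independent outcome per unit. Depending on how a programmer fills the table, the same data could give a spuriously small p-value, an uninformative comparison or, in the crossover, a p-value that is too large. An exploratory signal on delayed lows could then be claimed or missed because of a tabulation choice.

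**Working it through.** The documents give no figure for this endpoint to reproduce. The group size used below does reproduce: f² = 59/15² = 59/225 = 0.262, and one-way ANOVA power for three groups is 0.790 at 13 and 0.823 at 14 per group. The plan's 14 per group stands, and 48/3 = 16 per arm are randomized.

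**1. What the definition scores.** The window lasts 6 × 60 = 360 minutes. A subject who falls to 70 or lower at 23:50 and stays there past 06:00 is low for all 360 minutes and has 0 crossings. A trace that alternates just above and just below 70 adds one event at each fall. Onset before midnight is plausible on the protocol's own account: section 4.1 places post-exercise lows in young patients about 7-11 hours after vigorous afternoon exercise. If exercise ends at 16:00 (an assumption), that is 23:00-03:00.

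**2. Nights in scope.** Twelve weeks is 12 × 7 = 84 nights. At 2-3 sessions weekly (Protocol 8.4), 24-36 nights follow a session. The other 48-60 nights, 57-71% of the total, are outside the objective. In the CRC phase, sessions may be 2-28 days apart, and no rule says which nights belong to which dose.

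**3. Outpatient, nights tested as independent.** Within-subject correlation inflates the chi-square statistic by about DE = 1 + (m − 1) × ICC for m nights per subject. With three arms (2 df, critical value 5.991), the actual type I error is about exp(−5.991/(2 × DE)). The ICC and the nightly event probability (10-20%) are assumptions, not document figures. Beta-binomial simulations under no treatment effect, with 14 or 16 subjects per arm (24 nights: 14 per arm and a 20% nightly rate), agree with the formula:

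| Nights | ICC | DE | Formula | Simulation |
|---|---|---|---|---|
| 24 | 0.02 | 1.46 | 12.9% | 13% |
| 24 | 0.05 | 2.15 | 24.8% | 25% |
| 24 | 0.10 | 3.30 | 40.3% | 40% |
| 84 | 0.02 | 2.66 | 32.4% | 31-33% |
| 84 | 0.05 | 5.15 | 55.9% | 55-57% |
| 84 | 0.10 | 9.30 | 72.5% | 72-73% |

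At ICC 0 the night-level test keeps its level (about 5%). Testing crossings instead of nights was not simulated.

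**4. Outpatient, subjects with at least one event.** Over 84 nights, simulated type I error is 0.00-0.05, so there is no inflation. But 73-100% of subjects have an event. The 73% arises at a 10% nightly rate and ICC 0.20; at ICC 0.10 or less the share is 89-100%. With independent nights at 10%, the share is 1 − 0.9^84, above 99.9%. Nearly every subject falls in one cell.

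**5. Outpatient, per-subject proportion of nights by ANOVA.** Simulated type I error is 0.04-0.06 throughout.

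**6. CRC crossover, one night per period, unpaired test on subjects.** The variance of the paired difference is 2p(1 − p)(1 − ρ)/n, but the unpaired test assumes 2p(1 − p)/n. Chi-square therefore rejects only when |Z| > 1.96/√(1 − ρ):

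- ρ = 0.05: cut-off 2.01, type I error 4.4%
- ρ = 0.20: cut-off 2.19, type I error 2.8%
- ρ = 0.40: cut-off 2.53, type I error 1.1%

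Simulation with 48 subjects and event probability 0.15-0.30 (assumed) gives 0.01-0.05 for chi-square, 0.005-0.03 for Fisher and 0.04-0.05 for McNemar.

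**The case against.** The strongest reply is that the SAP never says nights or crossings are tested. Its general convention counts subjects, and the sentence on multiple instances only permits such an analysis. The table list has separate outputs for overnight hypoglycemia and for its incidence, which fits event counts in one and subject incidence in the other. On that reading there is no outpatient inflation. This stands, and it limits the conclusion. It does not settle the unit: SAP 4.3.6 uses incidence rate for a ratio of sessions and events, and the example code leaves the count undefined.

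A reader might infer that the planned p-values are far too small. The documents do not support that as a general statement. It needs nights or crossings to be the unit, and in the CRC phase a subject-level test errs the other way.

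A reader might also take this to be the main safety question of the trial. The endpoint is exploratory, is not among the safety variables in SAP 3, and Protocol 9.3.2 names no events of special interest.

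On scope, the protocol endpoint has no exercise restriction either, and the whole-study phrase may only mean that both phases share one definition. That is fair, but the objective is explicit about exercise, so the analysis set still needs a sentence. None of these replies removes the missed low at midnight, the absent recovery rule or the ignored pairing.

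**Conclusion.** Upheld as a defect of definition and specification on an exploratory endpoint.

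- **Certain from the text:** a low present at midnight that persists to 06:00 is not counted; repeat crossings count with no recovery rule; the definition is not tied to post-exercise nights; the unit tested is not stated; an unpaired test is named for a crossover.
- **Conditional:** outpatient type I error of about 13-40% (24 nights) or 32-73% (84 nights) applies only if nights are tested as independent, at an assumed ICC of 0.02-0.10. If subjects are tested, the level is kept but the comparison carries little information.
- **CRC phase:** on a subject-level reading the error is conservative, and more so as within-subject correlation rises.

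The primary conclusion is unaffected.

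**What to change.** Amend SAP 2.4 and 4.3.8 as follows.

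1. Score a night as an event if any CGM reading from 00:00 to 06:00 is at or below 70 mg/dL, including a subject already low at 00:00.
2. Use the night after any exercise session with study drug dosing. Keep nights after qualified sessions as a sensitivity analysis only: qualification depends on heart rate reached, duration and dose timing, all observed after randomization. Protocol 10.4.1 has sessions stopped at a reading of 70 or lower, so a session cut short by a low may fail to qualify, and this could differ by arm.
3. For each outpatient subject, compute the proportion of such nights with an event. Compare arms by the subject-level ANOVA/Kruskal-Wallis already planned for proportional time.
4. In the CRC phase, use the night after each session and a paired test such as McNemar.

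The cost is a few SAP sentences and minor reprogramming, with data already collected. Crossing counts become descriptive only. One limit remains: a yes/no night scores one isolated low reading the same as a six-hour low.
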